## 1. PROTOCOL SUMMARY

### 1.1. Synopsis

#### A Phase 3b, Multicenter, Randomized, Double-Blind, Placebo-Controlled Study Evaluating the Safety and Efficacy of Guselkumab Versus Placebo for the Treatment of Low BSA Moderate Plaque Psoriasis With Special Site Involvement

Guselkumab (Tremfya®) is a fully human immunoglobulin G1 (IgG1) lambda monoclonal antibody (mAb) that binds to the p19 subunit of human interleukin (IL)-23 with high specificity and affinity. The binding of guselkumab to the IL-23 p19 subunit blocks the binding of extracellular IL-23 to the cell surface IL-23 receptor thus inhibiting IL-23-specific intracellular signaling and downstream activation and cytokine production.

#### OBJECTIVES AND ENDPOINTS AND/OR ESTIMANDS

OBJECTIVES AND ENDPOINTS	
Primary Objective	Primary Endpoint
The primary objective of the study is to evaluate the clinical efficacy of guselkumab compared to placebo in participants with low body surface area (BSA) moderate plaque psoriasis with special site involvement.	The proportion of participants who achieve an Investigator's Global Assessment (IGA) score of cleared (0) or minimal (1) at Week 16
Secondary Objectives	Major Secondary Efficacy Endpoints
Efficacy To evaluate the efficacy of guselkumab compared with placebo in improving the signs and symptoms of psoriasis and patient-reported outcomes (PROs)	(The final ordering of multiplicity controlled major secondary endpoints will be specified in the Statistical Analysis Plan [SAP]) 
 
1. Change from baseline in BSA affected at Week 16
 
2. Change from baseline in total Psoriasis Area and Severity Index (PASI) score at Week 16
 
3. The proportion of participants who achieve an IGA score of cleared (0) at Week 16
 
4. The proportion of participants who achieve a PASI 90 response at Week 16
 
5. The proportion of participants who achieve a PASI 100 response at Week 16
 
6. The proportion of participants who achieve a scalp-specific IGA (ss-IGA) score of absence of disease (0) or very mild disease (1) at Week 16 among randomized participants with an ss-IGA score <math>\geq 3</math> at baseline
 
7. The proportion of participants who achieve a static Physician's Global Assessment of Genitalia (sPGA-G) score
 

	
of clear (0) or minimal (1) at Week 16 among randomized participants with an sPGA-G score <math>\geq 3</math> at baseline
 
8. The proportion of participants who achieve an intertriginous IGA (i-IGA) score of clear (0) or minimal (1) at Week 16 among randomized participants with an i-IGA score <math>\geq 3</math> at baseline
 
9. The proportion of participants who achieve a facial IGA (f-IGA) score of clear (0) or minimal (1) at Week 16 among randomized participants with an f-IGA score <math>\geq 3</math> at baseline
 
10. The change from baseline in Psoriasis Symptom and Sign Diary (PSSD) total symptom score at Week 16
 
11. The proportion of participants who achieve <math>\geq 4</math>-point reduction (improvement) in PSSD itch score from baseline at Week 16 among participants with a PSSD itch score <math>\geq 4</math> at baseline
 
12. The proportion of participants with PSSD Individual Symptom Scale Score = 0 at Week 16 among participants with PSSD <math>> 0</math> at baseline

Secondary Objectives
 
Safety
 
To evaluate the safety of guselkumab in participants with low BSA moderate plaque psoriasis with special site involvement
	
Safety Endpoints
 
 
The frequency and type of adverse events and serious adverse events
 

## HYPOTHESIS

It is hypothesized that guselkumab is superior to placebo in the treatment of low BSA moderate plaque psoriasis with special site involvement as assessed by the proportion of participants who achieve an IGA score of cleared (0) or minimal (1) at Week 16 (primary hypothesis).

## OVERALL DESIGN

This is a Phase 3b, multicenter, randomized, double-blind, placebo-controlled study designed to evaluate the efficacy and safety of guselkumab versus placebo in participants with low BSA moderate plaque psoriasis with special site involvement.

Approximately 300 eligible participants will be randomized 2:1 to receive either guselkumab CCI or placebo. Randomization will be stratified by qualifying special site (i.e., scalp, genital, intertriginous, and face), with approximately 25% of participants per each special site. If participants present with qualifying moderate psoriasis in multiple special sites, they will be allocated to the special site that is most severe, as determined by the participant. There will be 2 database locks (DBLs) in this study, at Weeks 16 and 56, to support reporting of short-and long-term efficacy and safety data, respectively. At the Week 16 DBL, unblinded data will only be made available to select Sponsor and Contract Research Organization (CRO) team members involved with analysis of the data and preparation of analyses for the Week 16 DBL. All other Sponsor, site, and CRO

personnel directly involved with study conduct will remain blinded to treatment assignments until the Week 56 DBL and related analyses have been completed.

## NUMBER OF PARTICIPANTS

Approximately 300 eligible participants will be randomized 2:1 to receive either guselkumab CCI C at Weeks 0 and 4 and then CCI or placebo.

## INTERVENTION GROUPS AND DURATION

There will be 2 treatment groups:

- A guselkumab group who will receive guselkumab CCI C at Weeks 0 and 4 and then CCI through Week 44. Placebo will be administered at Week 16 to maintain the blind.
- A placebo group who will receive placebo CC at Weeks 0, 4, and 12 after which they will cross over to receive guselkumab CCI at Weeks 16, 20, 28, 36, and 44.

## EFFICACY EVALUATIONS

Efficacy assessments will include evaluation of body surface area (BSA), Investigator's Global Assessment (IGA), Psoriasis Area and Severity Index (PASI), scalp-specific IGA (ss-IGA), facial IGA (f-IGA), intertriginous IGA (i-IGA), static Physician's Global Assessment of Genitalia (sPGA-G), Palmoplantar IGA (pp-IGA), and Nail Psoriasis Severity Index (NAPSI).

In addition, patient-reported outcomes (PROs) will include Psoriasis Symptom and Sign Diary (PSSD), Dermatology Life Quality Index (DLQI), Psoriasis Epidemiology Screening Tool (PEST), Psoriatic Arthritis Impact of Disease score (PsAID-12), and a Patient-Reported Outcomes Measurement Information System-29 (PROMIS-29) questionnaire.

## PHARMACOKINETIC AND IMMUNOGENICITY EVALUATIONS

Venous blood samples will be collected for measurement of serum concentrations of guselkumab and antibodies to guselkumab.

## PHARMACODYNAMIC AND BIOMARKER EVALUATIONS

Biomarker samples will be collected to examine the biologic response associated with blocking IL-23 and to identify biomarkers associated with psoriasis. Serum will be collected from all participants; skin biopsies and tape strips will also be collected from participants who consent separately to this component of the study.

## PHARMACOGENOMIC (DNA) EVALUATIONS

An optional pharmacogenomic blood sample will be collected from participants who consent separately to this component of the study to allow for pharmacogenomic research, as necessary where local regulations permit. The optional pharmacogenomic samples may be analyzed for identification of genetic factors that may be associated with psoriasis and/or the response to guselkumab.

## SAFETY EVALUATIONS

Safety assessments will consist of adverse events (including serious adverse events), physical examinations, vital signs, height and weight, electrocardiograms, clinical safety laboratory assessments, suicidal ideation or behavior using the Columbia-Suicide Severity Rating Scale, and concomitant medication review. Injection site reactions, hypersensitivity reactions, infections, tuberculosis evaluations, and pregnancy testing will be performed or collected as specified in the Schedule of Activities.

## STATISTICAL METHODS

A sample size of approximately 300 participants (200 participants on guselkumab and 100 participants on placebo) will allow at least 90% power to detect treatment effect differences of 45% between guselkumab (60%) and placebo (15%) for the primary endpoint with a 2-sided alpha level of 0.05. The sample size was also chosen to ensure an adequate number of participants with qualifying special site involvement (scalp, genital, intertriginous, and face). There will be approximately 25% of participants for each special site.

Descriptive statistics (e.g., mean, median, standard deviation [SD], interquartile [IQ] range, minimum, and maximum) will be used to summarize continuous variables. Counts and percentages will be used to summarize categorical variables. Graphical data displays (e.g., line plots) may also be used to summarize data.

[figure not shown]
Analyses suitable for categorical data (e.g., chi-square tests, Cochran-Mantel-Haenszel [CMH] chi-square tests, or logistic regression, as appropriate) will be used to compare the proportions of participants achieving selected endpoints (e.g., clinical response). In cases of rare events, the Fisher's exact test will be used for treatment comparisons. Continuous response parameters will be compared using analysis of variance (ANOVA), analysis of covariance (ANCOVA), or a mixed model for repeated measures (MMRM), unless otherwise specified. If the normality assumption is in question, an ANOVA or ANCOVA on the van der Waerden normal scores will be used. For time to event endpoints, survival analysis techniques will be used.

The primary endpoint will be analyzed based on the estimands defined in Section 9. The overall Type I error rate will be controlled at the significance level of 0.05 (2-sided) for the primary and major secondary endpoints. In order to control the overall Type 1 error rate, the primary endpoint and major secondary endpoints will be tested in a hierarchical fashion. That is, the first major secondary endpoint will be tested only if the primary endpoint is positive, and the subsequent endpoint(s) will be tested only if the preceding endpoint in the hierarchy is positive. The final ordering of major secondary endpoints will be specified in the final SAP. No multiplicity control will be made for other endpoints, and nominal p-values will be reported.

To compare the guselkumab group versus the placebo group for the primary endpoint, the CMH chi-square test (2-sided) stratified by special site will be used. The study will be considered successful if the test of the primary endpoint is positive at the 0.05 significance level.

## 1.2. Schema

Figure 1: Study Design Schematic

### 1.3. Schedule of Activities (SoA)

Phase	Screening a	Placebo b				Active Treatment b								Follow-Up b,c		
Week		0	4	8	12	16	20	24	28	32	36	40	44 (last dose)	48 (Final Efficacy)	Early Term.	56 (Final Safety)
Study Procedures d																
Screening																
Informed Consent e	X															
ICF for optional pharmacogenomics e	X															
ICF for optional skin biomarker substudy e	X															
Medical History	X															
Demographics	X															
Inclusion/exclusion criteria	X	X														
Study Intervention Administration																
Randomization		X														
IP administration		CCI														
Efficacy Assessments																
BSA	X	X	X	X	X	X	X	X	X	X	X	X	X	X	X	
IGA	X	X	X	X	X	X	X	X	X	X	X	X	X	X	X	
PASI	X	X	X	X	X	X	X	X	X	X	X	X	X	X	X	
ss-IGA (scalp)	X	X	X	X	X	X	X	X	X	X	X	X	X	X	X	
f-IGA (facial)	X	X	X	X	X	X	X	X	X	X	X	X	X	X	X	
i-IGA (intertriginous)	X	X	X	X	X	X	X	X	X	X	X	X	X	X	X	
sPGA-G (genitals)	X	X	X	X	X	X	X	X	X	X	X	X	X	X	X	
pp-IGA (palmoplantar)	X	X	X	X	X	X	X	X	X	X	X	X	X	X	X	
NAPSI (all 10 fingernails)	X	X	X	X	X	X	X	X	X	X	X	X	X	X	X	
Clinical Photographs (half body + 1 special site or target lesion) f	X	X	X	X	X	X	X	X	X	X	X	X	X	X	X	
Patient-reported Outcomes																
PSSD (7-day version)		X	X	X	X	X	X	X	X	X	X	X	X	X	X	
DLQI		X	X	X	X	X	X	X	X	X	X	X	X	X	X	

Phase	Screening a	Placebo b				Active Treatment b								Follow-Up b,c		
Week		0	4	8	12	16	20	24	28	32	36	40	44 (last dose)	48 (Final Efficacy)	Early Term.	56 (Final Safety)
PEST (no history of PsA and PEST negative at screening) g	X	X		X		X		X		X		X		X	X	
PsAID-12 (rheumatologist confirmed history of PsA or positive PEST at screening) g		X		X		X		X		X		X		X	X	
PROMIS-29		X		X		X		X		X		X		X	X	
Safety Assessments																
Full Physical Examination (including skin)	X													X	X	X
Vital signs	X	X	X	X	X	X	X	X	X	X	X	X	X	X	X	X
12-lead ECG	X															
TB evaluation	X	X	X		X		X		X		X		X	X	X	X
Chest X-ray h	X															
C-SSRS i	X	X	X	X	X	X	X	X	X	X	X	X	X	X	X	X
Urine pregnancy test j		X	X	X	X	X	X	X	X	X	X	X	X	X	X	X
Height		X						X						X	X	X
Weight		X						X						X	X	X
Clinical Laboratory Assessments																
Serum pregnancy test j	X															
TB IGRA k	X															
Hepatitis B and C serology l	X															
HIV Ab test	X															
Hematology	X	X	X		X	X		X		X				X	X	X
Chemistry	X	X	X		X	X		X		X				X	X	X
Lipid panel n		X						X						X	X	X
Hs-CRP		X	X			X		X		X				X	X	X
HbA1c		X						X						X	X	X

Phase	Screening a	Placebo b				Active Treatment b								Follow-Up b,c		
Week		0	4	8	12	16	20	24	28	32	36	40	44 (last dose)	48 (Final Efficacy)	Early Term.	56 (Final Safety)
Clinical Pharmacology and Biomarker Assessments p																
Serum guselkumab concentration		X	X			X				X				X	X	X
Anti-guselkumab antibodies		X	X			X				X				X	X	X
Serum biomarkers		X	X			X				X				X		
Optional Substudies e																
Skin biopsy p		X				X								X		
Tape stripping		X	X			X				X				X		
Whole blood (pharmacogenomics) q		X														
Ongoing Participant Review																
Concomitant therapy	X	X	X	X	X	X	X	X	X	X	X	X	X	X	X	X
Adverse events	X	X	X	X	X	X	X	X	X	X	X	X	X	X	X	X

a: The screening visit should occur within approximately 4 weeks before the Week 0 visit.

b: All post-baseline visits will have a visit window of  $\pm 7$  days counting from Week 0 as Day 1.

c: If a participant permanently discontinues study drug intervention prior to the Week 16 visit, they should be encouraged to return for all remaining study visits through Week 16, and the participant should also return for a final visit to perform assessments under the Week 56/final safety visit approximately 12 weeks after the last study intervention administration. If a participant permanently discontinues study drug at or after the Week 16 visit, they should complete the Week 48/final efficacy visit assessments at the time of discontinuation, or as soon as possible, and also return for a final safety visit to perform assessments under the Week 56/final safety visit approximately 12 weeks after the last study intervention administration.

d: All study procedures and evaluations should be completed before administration of study drug.

e: ICFs must be signed before the first study-related activity. The optional skin biopsy, tape stripping, and pharmacogenomics substudies will use separate ICFs.

f: Details may be found in the Photography Manual.

g: Participants with no prior diagnosis of rheumatologist confirmed PSA will complete the PEST at screening. If screening PEST score  $\geq 3$ , participants will complete PsAID-12 at Week 0 (baseline) and for the remainder of study visits as specified. If screening PEST score  $< 3$ , participants will complete PEST at Week 0 (baseline) and for the remainder of study visits as specified. Participants with prior diagnosis of rheumatology confirmed PSA will complete the PsAID-12 starting at Week 0 (baseline) and for the remainder of study visits as specified.

h: Chest X-ray should be performed at screening if the participant does not have a chest X-ray within 12 weeks prior to the first administration of study intervention.

i: All participant questionnaires should be completed before any other tests, procedures, or evaluations on the day of the visit for baseline and post-baseline visits. The 'Baseline/Screening' version of the C-SSRS will be performed at the screening visit prior to all questionnaires. At Week 0 and all subsequent visits, the 'Since Last Visit' version of the C-SSRS will be performed after all other questionnaires.

j: Participants of childbearing potential must have a negative pregnancy test before randomization and before study drug administration at study visits.

k: Interferon gamma release assay testing includes either QuantiFERON-TB® or T-SPOT.TB®. Interferon gamma release assay testing is not required at screening for participants with a history of treated latent TB or ongoing treatment for latent TB.

- l: For details related to hepatitis B screening and eligibility, refer to Appendix 3. For details related to hepatitis C screening and eligibility, refer to Exclusion Criterion 32.
- m: Laboratory tests are listed in Appendix 2 of the protocol.
- n: Participants must fast (i.e., no food or beverages [except water]) for at least 8 hours before blood is drawn for lipid panel unless there is medical contradiction. All other visits can be non-fasting.
- o: All blood samples must be collected before study agent administration at visits when a study agent administration is scheduled. Blood collected from 1 venipuncture will be divided into multiple aliquots of serum for the measurement of guselkumab concentration, antibodies to guselkumab, and a back-up sample. Biomarker blood collection will be divided into 3 aliquots. Details will be provided in the Laboratory Manual.
- p: Biopsy collection is optional. At Week 0, lesional and non-lesional skin samples will be collected; only lesional samples will be collected at all later timepoints. Refer to the biopsy manual for further details.
- q: The whole blood (pharmacogenomics) sample is optional and should be collected at the specified timepoint; however, if necessary, it may be collected at a later timepoint without constituting a protocol deviation.

Ab = antibodies; BSA = body surface area (affected); C-SSRS = Columbia-Suicide Severity Rating Scale; DLQI = Dermatology Life Quality Index; ECG = electrocardiogram; f-IGA = facial IGA; HbA1c = hemoglobin 1c; HIV = human immunodeficiency virus; Hs-CRP = high-sensitivity C-reactive protein; ICF = informed consent form; IGA = Investigator's Global Assessment; IGRA = interferon gamma release assay; i-IGA = intertriginous IGA; IP = investigational product; NAPSI = Nail Psoriasis Severity Index; PASI = Psoriasis Area and Severity Index; PEST = Psoriasis Epidemiology Screening Tool; pp-IGA = palmoplantar IGA; PROMIS-29 = Patient-Reported Outcomes Measurement Information System-29; PsA = psoriatic arthritis; PsAID-12 = Psoriatic Arthritis Impact of Disease score; PSSD = Psoriasis Symptom and Sign Diary; sPGA-G = static Physician's Global Assessment of Genitalia; ss-IGA = scalp-specific IGA; TB = tuberculosis; term. = termination

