## 6. STUDY INTERVENTION AND CONCOMITANT THERAPY

### 6.1. Study Intervention(s) Administered

Study intervention administration must be captured in the source documents and the electronic case report form (eCRF).

Guselkumab and placebo to match guselkumab will be manufactured and provided under the responsibility of the Sponsor. Refer to the guselkumab prescribing information for a list of excipients.

Detailed instructions on the administration of study intervention will be provided in the Site Investigational Product and Procedures Manual.

The 2 treatment groups will receive study intervention dosing and blinding administrations as below:

- Group 1 (guselkumab)
  - Guselkumab **CCI** **CC** at Weeks 0 and 4 and then **CCI** through Week 44
  - Placebo for guselkumab **CC** at Week 16
- Group 2 (placebo)
  - Placebo for guselkumab **CC** at Weeks 0, 4, 12
  - Cross-over to treatment with guselkumab **CC** at Weeks 16, 20, 28, 36, and 44

For a definition of study intervention overdose, refer to Section 6.7.

Guidelines for study intervention affected by the COVID-19 pandemic are provided in Appendix 8.

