### **8.2.10. Infections**

Investigators are required to evaluate participants for any signs or symptoms of infection at scheduled visits. Study intervention administration should not be given to a participant with a clinically significant, active infection. If a participant develops a serious infection, including but not limited to sepsis or pneumonia, discontinuation of study intervention must be strongly considered (Section 7.1). Any serious infection should be discussed with the medical monitor or designee, and study intervention should be withheld until the clinical assessment is complete.

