### Ongoing Tuberculosis Evaluation

To aid in the early detection of TB infection or exposure during study participation, participants must be evaluated for TB signs, symptoms, and close contacts at scheduled visits (refer to Section 1.3) or by telephone approximately every 4 to 12 weeks. The following series of questions is suggested for use during the evaluation:

- “Have you had a new cough of >14 days’ duration or a change in a chronic cough?”
- “Have you had any of the following symptoms:
  - Persistent fever?
  - Unintentional weight loss?
  - Night sweats?”
- “Have you had close contact with an individual with active TB?” (If there is uncertainty as to whether a contact should be considered “close,” a physician specializing in TB should be consulted.)

If the evaluation raises suspicion for TB infection or the participant has had a close contact exposure to TB, study intervention must be withheld and an immediate and thorough investigation must be undertaken, including consultation with a physician specializing in TB to determine if treatment is warranted prior to any further study intervention. Participants should be encouraged to return for all subsequent scheduled study visits according to the protocol.

**Note:** Investigators should be aware that TB reactivation in immunocompromised participants may also present as extrapulmonary or disseminated disease.

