### **8.3.2. Method of Detecting Adverse Events and Serious Adverse Events**

Care will be taken not to introduce bias when detecting AEs or SAEs. Open-ended and nonleading verbal questioning of the participant is the preferred method to inquire about AE occurrence.

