1.2. Study Design

This is a Phase 3b, multicenter, randomized, double-blind, placebo-controlled study designed to evaluate the efficacy and safety of guselkumab versus placebo in participants with low BSA moderate plaque psoriasis with special site involvement.

Approximately 300 eligible participants will be randomized in a 2:1 ratio to receive either guselkumab [REDACTED] at Weeks 0 and 4 and then [REDACTED] or placebo (Figure 1). Randomization will be stratified by qualifying special sites (i.e., scalp, face, intertriginous, and genital) with approximately 25% of participants per each special site. If participants present with qualifying moderate psoriasis in multiple special sites, they will be allocated to the special site that is most severe, as determined by the participant. The study will aim to enroll no less than approximately 20% of participants from diverse racial-ethnic backgrounds (i.e., self-identify as non-white/non-Caucasian descent) to reflect the North American Census population.

There will be 2 treatment groups:

- A guselkumab group who will receive guselkumab [REDACTED] [REDACTED] at Weeks 0 and 4 and then [REDACTED] through Week 44. Placebo will be administered at Week 16 to maintain the blind.
- A placebo group who will receive placebo at Weeks 0, 4, and 12 after which they will cross over to receive guselkumab at Weeks 16, 20, 28, 36, and 44.

Further details on active and blinding study intervention administrations for both treatment groups are provided in Section 6.

There will be 2 database locks (DBLs) in this study, at Weeks 16 and 56. After all participants have completed the Week 16 visit (or discontinued from the study), a Week 16 DBL will be performed, and unblinded data will only be made available to select Sponsor and Contract Research Organization (CRO) team members involved with analysis of the data and preparation of analyses for the Week 16 DBL. All other Sponsor, site, and CRO personnel directly involved

with study conduct will remain blinded to treatment assignments until the Week 56 DBL and related analyses have been completed. A diagram of the study design is provided in [Figure 1](#).

[figure not shown]
Week 0 through Week 16 (Placebo Controlled Period)

- Group I (n=200): guselkumab CCI CC at Weeks 0, 4, and 12. Placebo will be administered at Week 16 to maintain the blind.
- Group II (n=100): placebo at Weeks 0, 4, and 12 followed by guselkumab CCI at Weeks 16

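### The TB evaluation is scheduled at seven of the eight injection visits but not at Week 16, the placebo arm's first guselkumab dose: an optional, near-free improvement

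*Protocol*

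**What the plan says.** In the Schedule of Activities (Protocol 1.3), the row "TB evaluation" is marked at Screening, Weeks 0, 4, 12, 20, 28, 36, 44 and 48, Early Termination and Week 56. It is blank at Weeks 8, 16, 24, 32 and 40.

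Protocol 6.1 gives the placebo arm placebo at Weeks 0, 4 and 12, then guselkumab "at Weeks 16, 20, 28, 36, and 44". SAP 1.2 describes the guselkumab arm's placebo-controlled period as active drug "at Weeks 0, 4, and 12. Placebo will be administered at Week 16 to maintain the blind". Week 16 is therefore an injection visit for both arms.

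Protocol 8.2.11 requires participants to be evaluated for "TB signs, symptoms, and close contacts at scheduled visits (refer to Section 1.3) or by telephone approximately every 4 to 12 weeks". One of its suggested questions is "Have you had close contact with an individual with active TB". If TB is suspected, or if "the participant has had a close contact exposure to TB, study intervention must be withheld", and the matter must be investigated before any further dosing.

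**The concern.** At seven injection visits the dose and the TB questions fall on the same day. The exception is the visit at which up to about 100 placebo participants (the planned arm, less earlier dropouts) first meet the active drug. The guselkumab arm is asked on the day of its first active dose, Week 0. The placebo arm starts active drug on answers from Week 12.

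The gap is about exposure more than symptoms. The withholding rule in 8.2.11 works only when a contact is known, and nothing scheduled at Week 16 asks about one. A symptom-free participant who has had such a contact since about Week 12, and does not mention it, could be dosed without being asked.

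Up to Week 16 the marked weeks (0, 4, 12) coincide with the guselkumab arm's active doses. The row may have been built around that arm, but this is an inference.

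**Working it through.** No power or error-rate calculation is involved. The check sets the schedule against the dosing text.

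**Inputs**
- TB evaluation weeks: Protocol 1.3. The row has 16 cells for 16 visit columns, so each mark can be placed.
- Injection weeks: the investigational product row is redacted, but the placebo arm's dosing in Protocol 6.1 gives all eight: 0, 4, 12, 16, 20, 28, 36, 44.
- Visit window: ±7 days (Protocol 1.3, footnote b).

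**Step 1: match the two lists**

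| Injection week | 0 | 4 | 12 | 16 | 20 | 28 | 36 | 44 |
|---|---|---|---|---|---|---|---|---|
| TB evaluation | yes | yes | yes | **no** | yes | yes | yes | yes |

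Seven of eight are covered. The one missing is Week 16.

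**Step 2: test the protocol's own interval rule**

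The gaps between consecutive evaluations (0, 4, 12, 20, 28, 36, 44, 48, 56) are 4, 8, 8, 8, 8, 8, 4 and 8 weeks. All lie within 4 to 12 weeks. With ±1 week at each end, the Week 12 to Week 20 gap is 8 ± 2, or 6 to 10 weeks, which still complies.

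**Step 3: size the gap**
- Period not asked about before the first active dose: 16 − 12 = 4 weeks (2 to 6 with windows).
- Delay from that dose to the next scheduled questions: 20 − 16 = 4 weeks (2 to 6 with windows).
- Active doses given to the placebo arm between the Week 12 and Week 20 questions: 1.
- These ranges use visit windows only. Protocol 6.4 lets a dose be given within about 2 weeks of its scheduled visit, which widens them somewhat.

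**Step 4: what Week 16 already covers**
- Symptoms: Protocol 8.2.10 requires investigators to "evaluate participants for any signs or symptoms of infection at scheduled visits". Vital signs (including temperature), hematology, chemistry, hs-CRP and adverse event review are all marked at Week 16. TB symptoms are largely covered.
- Exposure: Protocol 8.3.2 says "Open-ended and nonleading verbal questioning of the participant is the preferred method to inquire about AE occurrence". That concerns events, not contacts, and is not a specific prompt. No other Week 16 item asks about contact.

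**Step 5: number affected**

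The documents give no rate of TB contact, so no estimate is possible. The planned 100 in the placebo arm is the group passing through this visit, not the number affected.

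**Step 6: after the change**

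Adding Week 16 covers eight of eight injection visits and splits the 8-week gap into 4 + 4 weeks.

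**The case against.** The strongest reply is that the schedule already meets its own standard. Section 8.2.11 sets an interval and does not tie the evaluation to each injection or to a first active dose. From Week 4 the row runs on a regular 8-week cycle, and Week 16 simply falls between two points of it. A guselkumab participant exposed just after an evaluation can go 8 weeks on drug before being asked again, whereas the placebo participant described here goes about 4 weeks on drug. The documents give no reason why a first dose should carry more TB risk than a later one.

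The absolute risk is also very low. Entry screening includes IGRA, chest imaging and an exclusion for recent contact (Protocol 5.2). The SAP's location subgroup (5.7.8) lists only the United States and Canada. Both earlier Phase 3 trials with a Week 16 crossover reported no active TB through 5 years (Protocol 2.2). The question set is only suggested wording, and participants may be told at consent to report contacts; the consent form was not available to check.

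All of this stands, and it is why the point is an improvement and not an error. It does not close the gap. The protocol treats contact as serious enough to exclude at entry and to stop dosing, yet asks about it at every injection visit except this one.

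**Conclusion.** The point holds as a low-priority suggestion. Week 16 is the only injection visit without a TB evaluation, and it is the placebo arm's first active dose. No protocol rule is breached, and no endpoint or efficacy analysis is affected.

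The consequence is bounded: for a symptom-free contact arising after about Week 12 and not volunteered, one active dose and about 4 weeks until the scheduled questions. The probability cannot be quantified and is likely very small. The argument for change is the near-zero cost, not the size of the risk.

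The conclusion assumes that the schedule row was extracted correctly and that no site instruction outside these documents already asks about contact at Week 16. Confidence is medium.

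**What to change.** Mark the TB evaluation at Week 16 in the Schedule of Activities for both arms, so that the blind is kept. Use the existing 8.2.11 questions, including the contact question, before the injection; footnote d already places evaluations ahead of dosing.

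The cost is one table cell and a few minutes at a visit that already takes place, with no sample and no extra visit. The downside is an occasional delayed dose while a positive answer is followed up, which is what the existing withholding rule intends.

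If the study is under way, include the change in the next amendment. The protocol reviewed is the original with no amendments, so the change may wait for one; the size of the risk makes that acceptable.
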